15.2.1. Process for Obtaining Informed Consent

The site is encouraged to use the study-specific Informed Consent Form supplied by Sponsor. The information that is given to the subject or the representative shall be in language understandable to the subject or the representative. Any changes to the ICF document must be reviewed by Sponsor and approved by the appropriate IRB to ensure that it meets all requirements before use by the center.

The person conducting the informed consent shall verbally explain the study to the potential subject, providing all pertinent information (e.g., purpose, procedures, risks, benefits, alternatives to participation, etc.), and must allow the potential subject ample opportunity to ask questions. The potential subject shall be provided with a written consent form and afforded sufficient opportunity to consider whether or not to participate in the research. After allowing the potential subject time to read the consent form, the patient should be given the opportunity to meet with an Investigator listed on the delegation of authority log to answer any additional questions he/she may have. Once a patient has had all his/her questions answered and has agreed to participate in the clinical investigation, the person conducting the informed consent shall ask the patient to personally date and sign the informed consent form. A copy of the signed informed consent form must be given to the subject and the original filed at the investigational site. The PI must ensure that the requirements for obtaining informed consent are met. The date in which the subject signature is obtained should be also reported in the source documentation (e.g. subject hospital chart). The consent form should be updated or amended whenever new information becomes available that may be relevant to the subject. In such case, the subjects shall be re-consented to the latest version.

Any violations of the informed consent process must be reported as deviations to the Sponsor and local regulatory authorities.

15.3. SITE AND INVESTIGATOR SELECTION CRITERIA

Sites will be selected to participate in this study if they have demonstrated sufficient experience with the implantation of the Perceval valve and are able to implement the requirements of the study protocol. In order to ensure appropriate physician and site participation, the criteria outlined in the Section 15.3.1 shall be met.

15.3.1. Site Selection Criteria

Sites selected to participate in this study shall meet the following criteria:

- Must have sufficient infrastructure to conduct a clinical study (including 4D CT-scan capabilities as specified by the Core Lab requirement).
- Must have experience with Electronic Data Capture system (EDC)

15.3.2. PI selection criteria.

The PIs selected to participate in this study:

- Must be experienced in the implantation of the LivaNova Perceval bioprosthetic aortic valve.
- Must have experience in clinical studies execution and knowledge of GCP.

Before participating in the study, all PIs must agree to respect and fulfill the terms of this investigational plan and sign an Investigator Agreement.

15.4. CIP ADHERENCE / CIP AMENDMENT

Except under emergency circumstances, the PI is not allowed to deviate from the protocol. Deviations to the investigational plan that are decided by the PIs to protect the rights, safety and well-being of human subjects, or are as a result of an incorrect application of the protocol, shall be documented and reported by the PI to the Sponsor as soon as possible.

Deviations affecting subject's safety and/or well-being will be promptly reported to the IRB. Any deviation from the investigational plan to protect life, or physical well-being of a subject in an emergency shall be reported within 5 days to the site's IRB and the Sponsor.

Any amendment to the protocol will be submitted to appropriate authorities for authorization or information depending on the nature of the change. Moreover, any administrative updates, not requiring a submission to the IRB will be documented. Administrative updates are defined as changes that will not impact the safety and well-being of the subjects nor the scientific value of the study. Examples include the following: change in the name of staff responsible for the study conduction as defined in the section "names and addresses", possible change in the legal entities or name of the Sponsor, and formatting or grammar edits.

15.4.1. Protocol Deviations

Principle Investigators of the study are not allowed to deviate from the protocol requirements. In particular, it is recommended to make every effort to avoid introduction of biases caused by protocol deviations. If a deviation still occurs, it shall be listed and reported in the appropriate eCRF.

The Sponsor will assess the seriousness of the deviation, classifying these as major or minor; and will present the list of the deviations to the SC. The final decision about the seriousness of the deviation will be assessed by the SC.

Major deviations are defined as departures from the protocol that may potentially compromise the subject's rights, safety, and well-being, or the completeness, accuracy, reliability, or scientific integrity of the data. Major and minor deviations will be validated before data lock and prior to the statistical analysis being performed.

15.4.2. Corrective and Preventive Actions, Investigator Disqualification Criteria

Deviations will be reviewed and evaluated on an ongoing basis and, as necessary, appropriate corrective and preventive actions may be investigated and put in place by the SC and/or Sponsor.

If a site fails to implement a corrective action, or in case of repeated non-compliance, the Sponsor may decide to discontinue enrollment at that site or to prematurely disqualify the site from the study.

15.5. MONITORING PROCEDURES, AUDITS AND INSPECTIONS

15.5.1. Study Monitoring

Study monitoring will be performed during the study by appropriately trained and qualified monitors to assess continued compliance with the protocol and applicable regulations. In addition, the monitors verify that study records are adequately maintained, that data are correctly reported (source data verification) with respect to timeliness, adequacy, and accuracy, and that the PI continues to have sufficient staff and facilities to conduct the study safely and effectively.

The PI guarantees the Sponsor's personnel, their designees, and any appropriate regulatory authorities direct access to original source documents.

The Sponsor monitoring procedures will be defined in a specific monitoring plan referring to responsibilities related to the study, including but not limited to site initiation, routine monitoring, in-house quality control, study close-out and securing compliance. The monitoring plan will describe the frequency and extent of monitoring, including the amount of source data verification required for the study.

15.5.2. Sponsor Audits and Inspections by Regulatory Agencies

The study may be subject to quality assurance audits by the Sponsor or designee, as well as inspection by appropriate regulatory authorities, in which case the Sponsor should be immediately notified. In case of a site audit, either by the Sponsor or legal authorities, the PI must allow the inspection. It is important that the PI and relevant study personnel are available during audits and that sufficient time is devoted to the process.

15.6. Role of Sponsor Representatives

Sponsor personnel can provide support to the PI as needed during the study, testing required by the protocol, follow-ups, and on-site troubleshooting if necessary. Support may include Investigative site training, addressing questions, or providing clarifications to investigative sites.

In addition, Sponsor personnel may perform certain activities to ensure study quality. These activities may include the following:

- Reviewing collected data and study documentation for completeness and accuracy
- On-site troubleshooting if necessary

Sponsor personnel will not do the following:

- Practice medicine
- Provide medical diagnosis or treatment to subjects
- Discuss a subject's condition or treatment with a subject without the approval and presence of the PI
- Independently collect study data (defined as safety or effectiveness endpoint data)
- Enter data in the investigative site electronic data capture systems

15.7. CURRICULUM VITAE

The PI will provide updated curriculum vitae with current position and evidence of required qualifications through education, training and experience.

15.8. INVESTIGATOR REPORTS

The PI must provide the following reports to a Sponsor or designee in a timely manner (for safety reports, refer to Section 12.1)

Table 8 Investigator Reporting Requirements

Report Type	Timeframe for Reporting	Report to:
Withdrawal of IRB approval	5 Working Days	Sponsor
Progress reports	At least Annually	Sponsor, IRB
Other reports	Upon Request	Sponsor, FDA, IRB, and/ or other regulatory agencies

15.9. DATA RETENTION

15.9.1. Investigator

The PI must retain all study records, including study case report forms, data clarification forms, and other supporting documentation. These records will be filed and archived at the Principal Investigator and Sponsor locations. Data will be retained at least 15 years after study closure, starting from the signature date of the study report.

15.9.2. Sponsor

It is the Sponsor's responsibility to inform the PI when documents no longer need to be maintained. The PI will take measures to ensure that these essential documents are not accidentally lost, damaged, or destroyed. If for any reason the PI withdraws responsibility for maintaining these essential documents, custody must be transferred to an individual who will assume responsibility and the Sponsor must receive written notification of this custodial change.

The Sponsor will maintain, organize and archive study documentation prior, during and after the study in accordance with established processes and procedures. Throughout the study and after, measures will be taken to prevent accidental or premature destruction of study documentation. Electronic data will be stored on the Sponsor's servers. For some EDC studies, raw data will be stored on the EDC provider servers.

16. CONFIDENTIALITY

Confidentiality of subjects' data and identity will be maintained for the length of the study and beyond.

All information and data sent to the Sponsor concerning study subjects or their participation in this study will be considered confidential by the Sponsor. Only authorized personnel of the Sponsor or an authorized representative shall have access to these confidential records. Authorized regulatory personnel have the right to inspect and copy all records pertinent to this study. Data collected during this study may be used by the Sponsor for the purposes of this study, for publications, to support future research, or for other business purposes. All data used in the analysis and reporting of this study shall include no identifiable reference to specific subject name.

17. PROPERTY RIGHTS

This protocol is property of the Sponsor. It should not be altered, used or disclosed to a third party without prior written consent.

18. DATA PROTECTION

The Sponsor is committed to uphold the local regulation relating to data management and data protection in biomedical research.

19. SUBJECTS' INSURANCE AND POTENTIAL COMPENSATION

Providing the present protocol is respected, the civil liability of the Sponsor and all its agents is underwritten by a policy taken out the Sponsor with CHUBB Insurance.

20. CLINICAL STUDY RESULTS

Clinical study results will be communicated to appropriate scientific communities at the appropriate timelines as well to the authorities according to local laws after completion or termination of the study.

The study will be registered on the ClinicalTrials.gov website and updated on a regular basis.

21. PUBLICATION POLICY

Study results will be pooled across all sites participating in the study for the purpose of preparing a single, multi-site publication that will be coordinated by the Sponsor. Preparation of the comprehensive publication will occur at study end, but the Sponsor may, at its discretion, coordinate an additional, interim publication. The order of authorship will be determined by the Sponsor and will be based in part on the number of CIP compliant subjects at each site.

The agreement of the Sponsor is mandatory before any publication.

- Authors will be selected based on participation and the quality of the data provided (deviations)
- Number of co-authors in the Authorship will be submitted to each Journal Authorship specific requirements.
- Sponsor must be cited in all publication and the Sponsor will have at least one name of the project team members in the list of primary authors.
- Any named author must meet all of the following standard criteria for authorship:
 - Substantial contributions to the conception or design of the work; or the acquisition, analysis , or interpretation of data; AND
 - Drafting the work or revising it critically for important intellectual content, AND
 - Final approval of the version to be published, AND
 - Agreement to be accountable for all the aspects of the work in ensuring that questions related to the accuracy of integrity of any part of the work are appropriately addressed and resolved.

A PI intending to publish results of the study must provide the Sponsor with a copy of any proposed publication, abstract, or presentation at least 60 days prior to submission for publication or presentation. The Sponsor shall have the right to object to the publication, abstract, or presentation if in the Sponsor's reasonable opinion such publication (i) contains Confidential Information; or (ii) will adversely affect any intellectual property or proprietary right of the Sponsor. In the event of an objection by the Sponsor the PI must either modify or delay the publication, abstract, or presentation for a period requested by the Sponsor not to exceed ninety to one hundred-twenty (90 to 120) days to permit the Sponsor to protect its interests.

22. LIST OF INVESTIGATORS

An updated list of PIs, investigation sites and potential institutions will be maintained by the Clinical Project Manager (or designee). The definitive list will be provided with the final clinical study report.

24. APPENDICES

Appendix 1 - ABBREVIATIONS & DEFINITIONS

Appendix 2 – ECHOCARDIOGRAPHIC PROTOCOL

Appendix 3 – CT SCAN PROTOCOL

Appendix 4 – American College of Cardiology Guidelines for Anticoagulation Therapy

APPENDIX 1: ABBREVIATIONS & DEFINITIONS

APPENDIX 2: ECHOCARDIOGRAPHIC PROTOCOL

APPENDIX 3: CT SCAN PROTOCOL

APPENDIX 4:

American College of Cardiology Guidelines for Anticoagulation Therapy

Study: APR002 BELIEVE

2 STUDY DESIGN

2.1 STUDY OBJECTIVES

2.1.1 Primary objective

The purpose of this study is to report the overall incidence of reduced leaflet motion identified by four-dimensional (4D), volume-rendered, computed tomography (CT) imaging in LivaNova Perceval bioprosthetic aortic heart valve up to 1 year post-implant on subjects that are off anticoagulation for at least 30 days.

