7.7. UNSCHEDULED VISITS

Unscheduled visits in symptomatic subjects (subjects with symptoms of reduced leaflet function) and any other subjects needing a study related follow-up visit that is not covered by the standard visit schedule. The following items may be captured:

- Subject status
- Physical evaluation (including cardiac rhythm and NYHA functional classification)
- Medications
- Transthoracic echocardiogram (TTE) (if available)
- SAEs

7.8. 2ND CT SCAN VISIT/REDUCED LEAFLET VISIT (AFTER THE 1ST CT SCAN, BUT PRIOR TO 1-YEAR FOLLOW-UP VISIT)

This visit is intended provide a 2nd follow-up 4D CT scan if the 1st CT scan showed reduced leaflet motion. This second CT scan visit is expected at approximately 6-10 months, but prior to 1 year follow-up. This follow-up evaluation shall be conducted in an office, hospital or clinic setting by the PI or his/her designee, at a time designated by the PI.

If the 1st CT scan showed no signs of reduced leaflet motion, a repeat 4D CT is not mandated and will only be done if it becomes clinically indicated. For subjects unable to undergo a contrast CT scan (e.g. inadequate renal function), a TEE may be performed.

The following data listed below shall be collected if this visit is required:

- Subject status
- Physical evaluation (including cardiac rhythm and NYHA functional classification)
- Medications

- Hemodynamic data from TTE examination measured at investigational site (MPG; PPG, EOA, aortic regurgitation with severity and location)
- CT scan with contrast
- TEE only in subjects that are unable to undergo CT scan at the time of follow-up
- Medications
- SAEs

7.9. 1-YEAR FOLLOW-UP VISIT

This visit is intended as a clinic visit at 1 year \pm 1 month after the day of the surgery. Follow-up evaluations shall be conducted in an office, hospital or clinic setting and are to be performed by the PI or his/her designee. **All efforts should be made to ensure that the subject comes to the clinic.**

The following data listed below shall be collected:

- Subject status
- Physical evaluation (including cardiac rhythm and NYHA functional classification)
- Medications
- Hemodynamic data from TTE examination measured at investigational site (MPG; PPG, EOA, aortic regurgitation with severity and location)
- Medications
- SAEs

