2.2 Overall study plan

Study main characteristics are described below. Please refer to the CIP for additional details.

- Prospective, interventional, multi-center study.
- Single-arm: subject implanted with Perceval aortic heart valve.
- Minimum of 75 asymptomatic and symptomatic subjects with evaluable 4D CT scans.
- Approximately 11 investigational sites where the devices are commercially available.
- Study duration: approximately 3 years (24 months for the enrollment phase and 1 year for the follow up phase).
- Blinding of CT scan imaging: (i) asymptomatic subjects and principal investigators (PIs) blinded from the CT imaging and Core Laboratory (Lab) findings; (ii) symptomatic subjects and the PI can be unblinded to CT imaging results; (iii) Core Lab blinded to subject status.
- Main assessments: (i) subject inclusion and implant data; (ii) hospital discharge (or 30-days after implant); (iii) anticoagulation (ACT) or dual antiplatelet therapy (DAPT) discontinuation (or Planning) visit (iv) first CT scan at minimum of 1 month after the discontinuation of ACT/DAPT; (v) second CT scan within 1 year post-implant for subjects in which reduced leaflet motion was previously detected; (vi) 1 year post-implant.

The visits are planned as reported in Figure 1

Figure 1: Schedule of Study Procedure

Procedure	Pre- Implant / Implant Data	Hospital Discharge	ACT / DAPT Discontinuation (or Planning) Visit	1 st CT-Scan Follow- up Visit	Reduced Leaflet Follow-Up (2 nd CT- Scan)	1 Year Follow- Up	Unscheduled Visits
Applicable Subjects	All Subjects	All Subjects	Subjects on ACT / DAPT	All Subjects	Subjects with Reduced Leaflet Motion on 1st CT Scan	All Subjects	Subjects with reduced leaflet function symptoms or other condition needing study related Follow-up
	After	≤ 30 days of Implant	1 – 6 mo.	Non-ACT/DAPT Pts. 30 days after Hospital Discharge (+ 60 day window)	6 – 10 mo.	1 year after the day of	At Discretion
	Successful Implant	ul (before the Po	Post-Implant (3 mo. preferred)	ACT/DAPT Pts. 30 days after ACT/DAPT Therapy discontinuation (+ 60 day window)	6 – 10 mo. Post-Implant	surgery (± 30 day window)	of Investigator

Study: APR002 BELIEVE

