10 PRIMARY ANALYSIS

10.1 Primary endpoint

The primary endpoint for the study is the incidence of reduced leaflet motion at a minimum of 30 days after the date of hospital discharge or ACT/DAPT discontinuation recorded on "Visit" e-CRF (expected within 1 to 6 months post-implant, preferably 3 months), as assessed by an independent Core Lab.

The valve leaflets will be assessed using 4D volume-rendered CT imaging or TEE for subjects unable to undergo CT scan (e.g. inappropriate renal function). Leaflet motion in all leaflets will be defined as normal, mildly reduced (<50% reduction in leaflet opening), moderately reduced (50-70% reduction in leaflet motion), severely reduced (>70% reduction in leaflet motion) and immobile (no or negligible leaflet motion).

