10.3 PRIMARY ENDPOINT DERIVATION

Reduced leaflet motion will be evaluated by means of the following parameters judged by Core Lab through the CT/TEE images:

Study: APR002 BELIEVE

- NL Orientation Left Motion
- NL Orientation Right motion
- NL Orientation Non Motion
- Rotated Left Non Motion
- Rotated Right Non Motion
- · Rotated Right Left Motion

Parameters will be judged by Core Lab as normal, mildly reduced (<50% reduction), moderately reduced (50 to 70% reduction), severely reduced (>70% reduction), or immobile (lack of motion in at least one valve leaflet).

No Reduction (success) of leaflet motion will be assigned if all of the above parameters will be recorded as normal or mildly reduced.

Reduction (failure) of leaflet motion will be assigned if at least one of the above parameters will be recorded as moderately reduced, severely reduced, or immobile.

Primary analysis will be based on results of the first CT scan as specified in the Table 2, using all subject in the SAF and done by overall.

Table 2: Use of CT scan results to define incidence in the primary analysis

Scenario #	Reduced leaflet motion at first CT scan	Primary Analysis
1	No	Not Reduction
2	Yes	Reduction

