10.5 SENSITIVITY ANALYSES

The analysis of the primary endpoints, which will provide incidence of reduced leaflet motion and its 90% CI, will be assessed in sensitivity analyses using different assumptions and populations (in each case, the same estimate and 90% CI calculation as specified in previous Section 10.4 will be applied):

COPYRIGHT LIVANOVA. ALL RIGHTS RESERVED. MAY NOT BE REPRODUCED WITHOUT PERMISSION. ALL HARD COPIES SHOULD BE CHECKED AGAINST THE CURRENT ELECTRONIC VERSION WITHIN MASTERCONTROL PRIOR TO USE AND DESTROYED PROMPTLY THEREAFTER. ALL HARD COPIES ARE CONSIDERED UNCONTROLLED DOCUMENTS.

LN-GLB-CLN-TEM-0033 rev1 Page 17 of 42

• Sensitivity Analysis 1: using the rationale to define the presence/absence of reduced leaflet motion as described in Table 3.

Study: APR002 BELIEVE

Table 3: Use of CT scan results to define incidence in the primary sensitivity analysis

Scenario #	Reduced leaflet motion at first CT scan	Reduced leaflet motion at second CT scan	Sensitivity Analysis 1
1	No	No	No Reduction
2	No	Yes	Reduction
3	Yes	No	No Reduction
4	Yes	Yes	Reduction

If the first CT scan showed no signs of reduced leaflet motion (scenario 1 and 2), a repeat exam is not mandated and will only be done if it becomes clinically indicated.

If no second CT scan will be performed, reduction/not reduction will be assigned as in Table 2.

- Sensitivity Analysis 2: using the PP population by excluding subject with major primary endpoint-related protocol deviations as described in Section 6.4.
- Sensitivity Analysis 3: Multiple Imputation (MI) analysis to adjust the primary analysis for the uncertainty introduced by the missing observations at first CT scan visit.

The objective of the MI (sensitivity analysis 3) is to impute reduction or no reduction for all subjects with missing values at first CT scan visit, and to perform this multiple time, so that the uncertainty or the imputation can be correctly accounted for in the analysis. Subject with missing data at first CT scan visit will have their missing value imputed according to *Missing At Random* assumptions and taking into consideration specific baseline characteristics.

The following steps will be carried out for the MI of missing data at first CT scan visit for the SAF set:

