11.2 INCIDENCE OF REDUCED LEAFLET MOTION IN SYMPTOMATIC AND ASYMPTOMATIC SUBJECTS

Study: APR002 BELIEVE

Incidence of reduced leaflet motion up to 1 year post-implant will be evaluated separately in symptomatic and asymptomatic subject using the same method described for the evaluation of the primary analysis.

Symptomatic are those subjects with clinical symptoms, such as, but not limited to shortness of breath, fatigue, or signs of thromboembolic events, as assessed by the treating physician.

A subject will be identified as symptomatic as will be recorded in "Subject Clinical Assessment" e-CRF at the first CT scan visit. List of symptomatic subjects will be reviewed and validated by study team reviewers and confirmed by Steering Committee before data lock.

Within each symptomatic/asymptomatic subgroup, subjects will be categorized on the basis of medication used and discontinued at least 30 days before the first CT scan: any, anticoagulant only, dual antiplatelet medications only, anticoagulant and dual antiplatelet medications.

A forest plot will be used to graphically represent the estimate point of the proportion together with its 90% CI in each category (medication used within symptomatic/asymptomatic subjects); number of subject with reduced leaflet motion and number of total subject in each category will be also displayed.

In addition, all CT or TEE parameters, results and units received from Core Lab (see Sections $\underline{10.3}$ and $\underline{12}$), will be summarized descriptively, as appropriate in the correspondent visit, by overall and subgroup defined in Section 5.3. Details on reference range lower and upper limits will be listed by marking any abnormality with a flag. Leaflet categories (normal, mildly reduced, moderately reduced, severely reduced and immobile) will be also summarized including actual number and percentages.

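### The primary objective and secondary endpoints 1 and 3 claim incidence of reduced leaflet motion up to 1 year, but subjects with a normal first CT are not routinely rescanned, so the main analyses estimate the proportion affected at the first evaluation

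*SAP*

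**What the plan says.** **Period claimed.** The primary objective covers the incidence "up to 1 year post-implant on subjects that are off anticoagulation for at least 30 days" (SAP 2.1.1). The protocol synopsis and Protocol 3.1 use the same one-year horizon. Secondary endpoints 1 (symptomatic and asymptomatic subjects) and 3 (relation to device, procedure or other causes) repeat it in the synopsis, Protocol 6.3.6 and SAP 11.1. SAP 11.2 states: "Incidence of reduced leaflet motion up to 1 year post-implant will be evaluated separately in symptomatic and asymptomatic subject using the same method" as the primary analysis.

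**What is measured.** The primary endpoint is read at a first scan "expected within 1 to 6 months post-implant, preferably 3 months" (SAP 10.1). SAP 10.3 is explicit: "Primary analysis will be based on results of the first CT scan as specified in the Table 2".

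**Who is scanned again.** The scheduled second CT at 6 to 10 months applies to "Subjects with Reduced Leaflet Motion on 1st CT Scan" (SAP 2.2, Figure 1). After a normal first CT, "a repeat 4D CT is not mandated and will only be done if it becomes clinically indicated" (Protocol 7.8). SAP 10.5 has the same rule: "a repeat exam is not mandated and will only be done if it becomes clinically indicated".

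**Imaging at 1 year.** Protocol 7.9 lists "Hemodynamic data from TTE examination measured at investigational site" and neither CT nor TEE.

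**The concern.** An incidence through one year requires that new cases arising during the year can be seen. Here a subject with a normal first CT has no later scheduled imaging that could show reduced leaflet motion. Protocol 2.1 reports that transthoracic echo missed the finding, that affected subjects were hemodynamically stable when it was detected, and that their gradients were statistically similar to those of subjects with normal motion. Clinical indication is therefore a weak trigger for finding new cases.

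At stake is the wording of the conclusion. A report that follows the objective would present a first-scan proportion as a one-year risk of a safety-relevant finding. If any onset occurs after the first scan, that figure is too low for the period it names.

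**Working it through.** **1. The plan's own precision figure (SAP 2.3, Protocol 10.2).** Inputs: 75 evaluable scans, exact two-sided 90% interval, width below 13% when the sample proportion is below 10%, 15% attrition.
- Exact binomial limits for 7/75 = 9.33%: 4.46% to 16.82%, width 12.35 points.
- At a proportion of exactly 10% (x = 7.5, not attainable, used only as the boundary): width 12.69 points.
- Enrolment: 75 / 0.85 = 88.2, consistent with approximately 88.

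The stated precision reproduces. It describes one proportion per subject at the first scan.

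**2. Which scan feeds each output labelled up to 1 year.**
- *Primary analysis:* first CT only (SAP 10.3, Table 2).
- *SAP 11.2:* the primary method. Symptom status is taken at the first CT visit, and medication groups are defined relative to the first CT.
- *SAP 11.4:* names no scan. Protocol 10.1.4 says the one-year incidence proportion uses the primary-endpoint method, and it lists the device, procedure and other-cause analysis under that sentence.
- *Kaplan-Meier of leaflet motion (SAP 11.5):* labelled up to 1 year, but follow-up ends at the first leaflet evaluation.

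**3. Size of the unobserved part.** With 7 positives of 75, 75 − 7 = 68 subjects (68/75 = 90.7%) have no scheduled CT after the first.

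**4. Illustration.** Let c be the share of first-CT negatives who develop reduced motion by 1 year. The documents give no value, so c is an assumption shown over a range. True one-year proportion = (7 + 68c)/75.

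| c (assumed) | Calculation | True one-year figure | Primary analysis reports |
|---|---|---|---|
| 0% | 7/75 | 9.3% | 9.3% |
| 5% | (7 + 3.4)/75 | 13.9% | 9.3% |
| 10% | (7 + 6.8)/75 | 18.4% | 9.3% |

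**5. Would indicated rescans recover it?** Assume 10% to 25% of converters are rescanned on clinical indication, and count any positive scan. With c = 5% the observed figure would be (7 + 0.34)/75 = 9.8% to (7 + 0.85)/75 = 10.5%, against a true 13.9%.

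**6. Is Sensitivity Analysis 1 a one-year figure?** Table 3 in SAP 10.5 codes a positive first and negative second scan as no reduction. If 3 of the 7 positives resolved (assumed) and no negative turned positive on rescan, it would report 4/75 = 5.3%, although 7/75 = 9.3% had been affected. It follows status at the last available scan and can fall below the primary result.

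**7. Precision for a one-year quantity.** With n = 75 the exact 90% width is 14.6 points at 14.5% and 16.1 points at 19.0%. The plan's width statement is conditional on a proportion below 10%, so it need not carry over to a true one-year incidence.

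**The case against.** The strongest reply is that the primary estimand is already clear. The endpoint, its derivation and its analysis are all tied to the first CT, the study is declared descriptive (Protocol 10), and the one-year phrase in the objective could be read as the outer limit for when the scan may occur. The visit window guide supports a wide range: discontinuation by day 180 plus up to 240 days puts a first CT as late as day 420. This stands to the extent that the primary analysis itself is not faulty. It does not rescue the word incidence, because one scan per subject at varying times is still a proportion at that scan, and it does not explain the same label on secondary endpoints 1 and 3.

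A second reply is that the reference to the primary method in SAP 11.2 may mean only the exact binomial interval. For 11.2 this is weak, since symptom status and medication groups are fixed at the first CT. For 11.4 it has more force: that section names no scan, and the first-CT reading comes from Protocol 10.1.4.

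A reader might also infer stronger claims that the documents do not support:
- *That first-CT negatives are never rescanned.* Indicated rescans are allowed, and a positive one counts as reduction in Sensitivity Analysis 1.
- *That all secondary endpoints fail.* Endpoint 2 rests on the scheduled second CT in first-CT positives. The safety, NYHA and TTE endpoints are followed to 1 year.
- *That every planned output would show the same figure whatever happens later.* This is true of the primary analysis; Sensitivity Analysis 1 can move in either direction.
- *That Sensitivity Analysis 1 already supplies an any-scan lower bound.* Table 3 rules that out.

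**Conclusion.** The point holds as a mismatch between label and measurement. The primary objective and secondary endpoints 1 and 3 name a one-year incidence. The primary analysis and SAP 11.2 deliver the proportion affected at the first evaluation; Protocol 10.1.4 directs SAP 11.4 to the same method, and the Kaplan-Meier in SAP 11.5 stops at that evaluation. The sample-size arithmetic is right for the first-scan proportion.

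The shortfall against a true one-year figure cannot be known from the documents. In the illustration it is 0, 4.5 (13.9 − 9.3, from unrounded values 13.87 − 9.33) or 9.1 percentage points (18.4 − 9.3), and it rests wholly on the assumed late-onset rates. The conclusion itself does not depend on those rates: whatever they are, the design does not observe late onset systematically.

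**What to change.** Restate the objective (Protocol synopsis and 3.1, SAP 2.1.1), secondary endpoints 1 and 3 (Protocol synopsis, 6.3.6 and 10.1.4, SAP 11.1), and the outputs of SAP 11.2, SAP 11.4 and the leaflet-motion Kaplan-Meier in SAP 11.5 along these lines:

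*Proportion with reduced leaflet motion at the first CT (or substitute TEE) evaluation, at least 30 days after ACT/DAPT discontinuation, or after hospital discharge for subjects discharged off therapy.*

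Name the scan used in SAP 11.4. Report the distribution of time from implant to first scan. That time is not fixed by the documents: the schedule of procedures gives 30 days with a 60-day window after discontinuation, while the visit window guide gives 60 to 240 days, and the two must be reconciled.

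If any figure up to 1 year is kept, count a subject as affected when any scan is positive and label the result a lower bound. Table 3 should not be used for this, because it recodes first-positive, second-negative subjects as having no reduction.

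The cost is a change of wording and table titles, one descriptive summary of scan timing and, if the optional figure is kept, one extra derivation. The claim becomes narrower. No extra scans or subjects are needed.
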